#### 9.5.3.4 Vital Signs and Weight

Detailed timing of vital sign and weight measurements is described in Section 2.1.

Vital signs (blood pressure, heart rate, respiratory rate, temperature) will be measured at all clinic visits. Vital signs will be measured pre- and post-infusion on Day 1 and Week 3 (all patients), pre- and post-infusion at Week 24 and Week 27 (proptosis non-responders who elect to receive open-label TEPEZZA) and pre-infusion on all other infusion days. In addition, if immediate infusion-associated events are noted during the infusion, vital signs will be monitored every 5 minutes until stable and then every 15 minutes for 2 additional determinations. Also, vital signs will be monitored every 15 minutes from the start of the infusion through 60 minutes after infusion completion for any subsequent infusions after the previous occurrence of immediate or delayed infusion-associated events.

Blood pressure and pulse measurements will be obtained with the patient's arm unconstrained by clothing or other material and while the patient is sitting up. When possible, the same arm will be used for measurements at all trial visits.

Weight will be measured at Screening and Weeks 9 and 24 (or PW1) (all patients) and Weeks 33 and 48 (or PW2) (proptosis non-responders who elect to receive open-label TEPEZZA). The dose on Day 1 and Weeks 3, 6 and 9 of the double-masked Treatment Period will be based on the Screening weight; weight measured at Week 9 will be used in dose calculations at Weeks 12, 15, 18 and 21. The dose on Weeks 24, 27, 30 and 33 of the open-label Treatment Period will be

based on the Week 24 weight; weight measured at Week 33 will be used in dose calculations at Weeks 36, 39, 42 and 45.

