### 9.5.6.2 Double-masked Treatment Period

#### 9.5.6.2.1 Day 1

On Day 1, patients will return to the clinic for Baseline assessments and the first dose of trial drug.

- Determine trial eligibility through review of the inclusion/exclusion criteria (see Section 9.3).
- Review medical history.
- Obtain signed, written informed consent for optional photographic analysis if not obtained at Screening; the consent must be obtained prior to photographs being obtained.
- Obtain predose blood samples for hematology and fasting chemistry (including thyroid and HbA1c) analysis.
- Collect predose blood samples for PK analysis, immunogenicity and **CCI** [REDACTED] testing.
- Collect predose urine sample for a pregnancy test for females of childbearing potential; the pregnancy test must be negative for the patient to receive trial drug.
- Inquire about AEs and prior medication use (see Table 9.1 for restrictions regarding medications).
- Perform predose visual acuity assessment.
- Perform predose Baseline efficacy assessments (proptosis, **CCI** [REDACTED] and GO-QoL questionnaire).
- Perform predose Baseline CAS.
- Take predose photograph of the patient's eyes for those patients who have consented.
- Record vital signs prior to and at the end of the infusion. Additional vital sign monitoring may be performed in the event of infusion-associated AEs (see Section 9.5.3.4 for details).

- Register enrollment in EDC in order for the unmasked site personnel to obtain randomization assignment, calculated trial drug dose, vial assignment (if applicable) and volume of trial drug to be administered.
- Administer trial drug and record date, volume and start/stop times of the infusion. Monitor the patient for any AEs during the infusion and for 60 minutes after the completion of the infusion.
- Collect post-dose blood samples for PK analyses following the end of the infusion.
- Enter visit data in the EDC system.

Patients will be discharged from the site after all Day 1 procedures have been completed, instructed to return for a clinic visit in 3 weeks and contacted the following day to perform a safety check following the first infusion.

#### 9.5.6.2.2 Week 3

- Collect predose urine sample for a pregnancy test for females of childbearing potential; the pregnancy test must be negative for the patient to receive trial drug
- Inquire about AEs and concomitant medication use.
- Collect predose blood samples for PK analysis, immunogenicity and CCI [REDACTED]

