5.4.2 Baseline and TEPEZZA Baseline

The following two definitions of Baseline will be used for analysis purposes:

- Baseline will be defined as the last observation before the first dose of study drug (TEPEZZA or Placebo). Baseline will be used for all applicable analyses during the double-masked treatment period.

- TEPEZZA Baseline will be defined as the last observation before the first dose of TEPEZZA whether it occurs in the double-masked treatment period or open-label treatment period. TEPEZZA Baseline will be used for applicable analyses during the open-label treatment period.

Change from Baseline (or TEPEZZA Baseline) is defined as the post-baseline value minus the Baseline (or TEPEZZA Baseline) value for the given assessment.

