5.4.3 Visit Windows for Analysis

For analyses that present visit-based data, the variables will be summarized based on the scheduled visits with derived analysis visit windows, with the exception of PK data, anti-drug antibody (ADA)/neutralizing antibody (NAb) data, and **CCI** [REDACTED], which will be analyzed based on nominal visits. For the visits on and after the first dose date, the actual visit date will be mapped to the derived analysis visit windows based on the study day.

Visit windows have been constructed so that every observation (unscheduled visits included) collected can be allocated to the scheduled analysis visit for planned analyses. The actual assessment day will be mapped to the windows defined for each scheduled study visit with following rules.

For multiple non-missing continuous measurements:

- If more than 1 assessment falls within a visit window, the closest non-missing valid assessment to the scheduled day will be used in the analysis.
- If 2 non-missing assessment actual dates are equidistant from the target day, the later visit will be used in the analysis.
- If there is more than 1 record on the selected day and the time is not recorded, the average will be taken, unless otherwise specified.
- For retest values of laboratory data, the retest value (the last valid observation assessed on the same visit day) will be chosen.

For multiple non-missing categorical measurements:

- For Baseline, the last available record on or prior to the date of the first dose of study drug will be selected. If there are multiple records with the same time or no time recorded on the same day, the value with the lowest severity will be selected (e.g., normal will be selected over abnormal for hematology).
- For postbaseline visits, if there are multiple records with the same time or no time recorded on the same day, the value with the worst severity within the window will be selected (e.g., abnormal will be selected over normal for hematology).

The Analysis Visit Window for the primary endpoint (change of proptosis), other endpoints (**CCI** [REDACTED]) and exploratory endpoint (**CCI** [REDACTED]) is shown in **Table 1**. The details for the other analysis visit window rules will be included in the TLF shell document.

Table 1 Analysis Visit Windows for Primary Endpoint

Analysis Visit	Target Study Day of Visit	Analysis Visit Window
Baseline	1	Non-missing assessment on or before the first dosing date (randomization)
Week 3	22	Day 2 to 32

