10.3 Vital Sign and Weight Measurements

Vital signs measurements will include systolic and diastolic blood pressures, heart rate, respiratory rate, height, weight, BMI and temperature.

Descriptive summaries of observed and change from Baseline values will be presented for each vital sign parameter by treatment group and visit for each treatment period.

A summary table for weight loss and a shift table for hypertension by NCI-CTCAE grade will be generated by treatment group and visit for each treatment period.

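### The SAP's date-based rule for categorical Baseline conflicts with its pre-dose definition of Baseline and can admit the Day 1 post-infusion blood pressure into the hypertension shift table

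*SAP*

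**What the plan says.** SAP 5.4.2 gives the general definition: "Baseline will be defined as the last observation before the first dose of study drug (TEPEZZA or Placebo"). It adds that "Baseline will be used for all applicable analyses during the double-masked treatment period", and makes no exception for categorical variables.

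SAP 5.4.3, on choosing among several non-missing categorical records, gives a different criterion: "For Baseline, the last available record on or prior to the date of the first dose of study drug will be selected". If records on the same day share a time or have no time, "the value with the lowest severity will be selected"; the example given is a haematology result, where normal is preferred to abnormal.

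Protocol 9.5.3.4 schedules two readings on the first dosing day: "Vital signs will be measured pre- and post-infusion on Day 1 and Week 3 (all patients"). The Day 1 procedures in Protocol 9.5.6.2.1 agree: "Record vital signs prior to and at the end of the infusion".

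SAP 10.3 plans the output in which the choice matters: "a shift table for hypertension by NCI-CTCAE grade will be generated by treatment group and visit for each treatment period".

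**The concern.** One section defines Baseline by the dose and the other selects it by the date. For most assessments the two give the same record, because Day 1 assessments are done before dosing. Vital signs are the exception, since a reading after the infusion is scheduled on the same date for everyone. A programmer who treats 5.4.3 as the more specific instruction would take that later reading.

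A Baseline grade measured after the infusion already contains any acute effect of it. Protocol 9.4.6.3.2 lists a transient rise in blood pressure among immediate infusion-associated events. Patients who have such an event are measured every 5 minutes until stable and then twice more at 15-minute intervals, so their last Day 1 record could come from the event or its aftermath. The shift table would then describe change from a treated state, and its content would depend on a programming choice that the SAP leaves open.

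**Working it through.** The plan states no figure on this point, so the check compares the texts.

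**Which Day 1 blood pressure becomes Baseline under each rule**

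| Rule applied | Record used |
|---|---|
| SAP 5.4.2 | Pre-infusion reading |
| SAP 5.4.3 categorical rule, times recorded | Last reading of the day, that is, post-infusion |
| SAP 5.4.3 categorical rule, no times | Lower grade of the two readings, from either one |
| SAP 5.4.3 continuous rule, no times | Average of the two readings |
| SAP 5.4.3 continuous rule, times recorded | Not specified for two readings on the same day |

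Only 5.4.2 gives an unambiguous pre-infusion value.

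**Does the categorical rule reach this table?** SAP 10.3 does not say whether the grade is selected as a categorical record or derived from a blood pressure already selected as continuous. The haematology example in 5.4.3 is itself a category derived from a continuous measurement, so a CTCAE grade for blood pressure plausibly falls under the same rule. If it does not, the continuous rule applies, and that can average in the post-infusion value.

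**What else is exposed?** Protocol 9.5.6.2.1 schedules proptosis, CAS, GO-QoL, visual acuity and laboratory samples before the dose on Day 1. Weight is measured at Screening and not on Day 1 (Protocol 9.5.3.4). That leaves blood pressure and the other vital signs.

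**Illustration of direction, all values assumed.** The documents give no blood pressure distribution, infusion effect or grade limits. Take a patient's true systolic pressure T as normal with mean 125 and SD 14 mmHg, and each reading's error e as normal with SD 7. Let pre = T + e1, post = T + d + e2 and later visit = T + 5 + e3, where d is the rise during infusion, the same in every patient. Let g(x) be the number of cut points, among 120, 140 and 160, that x reaches. The quantity of interest is the share with g(later) above g(Baseline), from 400,000 draws per row:

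| d (mmHg) | Baseline = pre | Baseline = post | Baseline = lower grade | Pre and post grades differ |
|---|---|---|---|---|
| 0 | 29.8% | 29.7% | 40.3% | 33.1% |
| 5 | 29.8% | 17.9% | 34.7% | 38.4% |
| 10 | 29.7% | 9.1% | 31.5% | 49.9% |
| 15 | 29.8% | 3.8% | 30.3% | 64.3% |

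With no infusion effect, the pre- and post-infusion choices give the same share. With a rise, the post-infusion Baseline shows fewer upward shifts. The lowest-severity rule works the other way: at d = 0 it adds 40.3 − 29.8 = 10.5 percentage points. If pressure fell during infusion, the post-infusion Baseline would show more upward shifts.

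**The case against.** The strongest reply is that 5.4.2 already settles the matter. It defines Baseline as pre-dose for all applicable double-masked analyses, and the 5.4.3 bullet can be read as choosing only among records that already meet that definition. This is a fair reading, and probably the intended one. It does not remove the conflict, because 5.4.3 states its own criterion and does not refer back to 5.4.2.

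A second reply is that Table 1 covers the primary and certain other endpoints, and that SAP 5.4.3 leaves the remaining visit-window rules to the TLF shells, which are not among these documents. The shells may restrict vital signs to pre-infusion records. That possibility stands, but the rule written in the SAP should not need another document to correct it.

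A reader might infer that the hypertension table will start from an on-drug value in all 57 patients and will hide blood pressure rises in the TEPEZZA arm. The documents do not support this, for four reasons:

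- The post-infusion reading is used only if 5.4.3 is applied over 5.4.2. Even then, a grade changes only where the two readings fall in different grades.
- In the placebo arm the reading follows saline, not drug.
- The direction is open. Protocol 9.5.3.1.1.5 lists hypotension among infusion-related symptoms, and no average effect on blood pressure is given.
- Infusion reactions are collected and summarised as adverse events of special interest (SAP 10.1.6), and their signs and symptoms are listed (SAP 10.1). They do not depend on this table to be seen.

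A reader might also extend the point to the open-label period. SAP 5.4.2 defines TEPEZZA Baseline as the last observation before the first TEPEZZA dose, and the date-based bullet in 5.4.3 refers only to the first dose of study drug. No competing rule applies to TEPEZZA Baseline.

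**Conclusion.** The conflict between SAP 5.4.2 and 5.4.3 is real but minor. A rule as written can yield a post-infusion Baseline in a planned safety table, contrary to the SAP's own definition. The conclusion assumes that the CTCAE blood pressure grade is selected under the categorical rule and that reading times are recorded. If times are missing, the post-infusion reading remains eligible through the lowest-severity rule. If blood pressure is handled as continuous and untimed, it enters through averaging.

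The reach is the hypertension shift table and, through averaging, the vital-sign change-from-Baseline summaries. These are descriptive, since SAP section 10 plans no hypothesis tests on safety data. Neither the size nor the direction of any distortion can be obtained from the documents; the simulated shares rest wholly on assumed values. The primary endpoint and its Baseline are not affected.

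**What to change.** Reword the categorical Baseline bullet in SAP 5.4.3 to select *the last available record before the start of the first infusion of study drug*, and state that records labelled post-infusion are excluded. This brings it into line with 5.4.2. Apply the same pre-dose restriction where same-day continuous vital signs are selected or averaged for Baseline. Where no time was recorded, the scheduled pre- or post-infusion label can identify the record. Leave the definition of TEPEZZA Baseline as it stands.

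The cost is about one line of SAP text and a matching check in the vital-sign programming specification. No data collection, sample size or efficacy analysis changes.

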3.1 Overall Study Design and Plan

This is a randomized, double-masked, placebo-controlled, parallel-group, multicenter trial. Patients will be screened for the trial within 4 weeks prior to the Baseline (Day 1) Visit. Approximately 57 patients who meet the trial eligibility criteria will be randomized on Day 1 in a 2:1 ratio to receive 8 infusions of TEPEZZA (10 mg/kg for the first infusion and 20 mg/kg for the remaining 7 infusions) or placebo once every 3 weeks (q3W). All patients will enter a 24-week double-masked treatment period, during which trial drug will be infused on Day 1 (Baseline) and Weeks 3, 6, 9, 12, 15, 18 and 21 (with a final visit at Week 24 of the 24-week treatment period).

At the end of the double-masked treatment period (Week 24), all patients will be assessed for treatment response. The primary treatment response is assessed based on the change in proptosis from Baseline. Proptosis responders were defined as patients with a 2 mm or greater reduction in proptosis from Baseline in the study eye, without deterioration (i.e., 2 mm or greater increase) of proptosis in the fellow eye. Proptosis non-responders who have completed the double-masked treatment period may choose to receive 8 infusions of TEPEZZA (10 mg/kg for the first infusion and 20 mg/kg for the remaining 7 infusions) in an open-label fashion q3W at Weeks 24, 27, 30, 33, 36, 39, 42 and 45. These patients will return to the clinic at Week 48 for End-of-Treatment assessments, and patients will be contacted by phone/email 30 days after the Week 48 Visit for safety assessment. Proptosis responders, as well as non-responders who choose not to receive TEPEZZA in an open-label fashion, will enter a 30-day Follow-up Period, during which study drug will not be administered. These patients will be contacted by phone/email 30 days after the Week 24 Visit for safety assessment.

An overview of the trial design is presented in **Figure 1**, and details of trial activities are presented in Section 15.1, Schedule of Assessments.

Figure 1 Schematic of Trial Design

Screen	BL	Double-masked Treatment Period TEPEZZA or Placebo ^{1,2} 24 Weeks										Open-label Treatment Period ² (Proptosis Non-responders who Choose to Receive Open-label TEPEZZA)							30-day Follow- up Period ²					
		*	*	*	*	*	*	*	*	*	*	*	*	*	*	*	*	*	*	*	*	*	*	*
4 weeks predose	Day 1 ³	W3 ³	W6	W9	W12	W15	W18	W21	W24 ^{3,4,5}	W27 ³	W30	W33	W36	W39	W42	W45	W48 ³							

Randomization¹ <———— Trial Week —————>

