* Infusion of trial drug (TEPEZZA or placebo in double-masked treatment period and open-label TEPEZZA in open-label treatment period).

BL=Baseline; q3W=once every 3 weeks; W=Week.

1. Patients will be randomized in a 2:1 ratio to receive:
 - a. TEPEZZA (10 mg/kg on Day 1 followed by 20 mg/kg q3W for the remaining 7 infusions); or
 - b. Placebo (placebo q3W for all 8 infusions).
2. Visit windows are ± 3 days for Weeks 3, 6, 9, 12, 15, 18 and 21 of double-masked treatment period and Weeks 27, 30, 33, 36, 39, 42 and 45 of open-label treatment period, and ± 7 days for Week 24 of double-masked treatment period, Week 48 of open-label treatment period and 30-day Follow-up Period.
3. All patients will be contacted by phone/email the day after infusion for the first and second infusions during the double-masked treatment period and during the open-label treatment period, and thereafter as deemed appropriate; additional phone/email contacts will occur the day after any clinic visit where a patient experiences an infusion-related adverse event.
4. Patients who are proptosis non-responders at Week 24 of the double-masked treatment period will be offered the option to receive 8 infusions of TEPEZZA (10 mg/kg on Day 1 followed by 20 mg/kg for the remaining 7 infusions) in an open-label fashion.
5. All patients will be contacted via phone or email 30 days (± 7 days) following the Week 24 (responders and non-responders who choose not to receive open-label TEPEZZA) or Week 48 (non-responders who receive open-label TEPEZZA) Visit.

[figure not shown]

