Week 6	43	Day 33 to 64
Week 12	85	Day 65 to 106
Week 18	127	Day 107 to 148
Week 24	169	Day 149 to 179*
Week 27	190	Day 180 to 200
Week 30	211	Day 201 to 232
Week 36	253	Day 233 to 274
Week 42	295	Day 275 to 316
Week 48	337	≥ Day 317

* For patients who did not enter the open-label treatment period, Week 24 analysis visit window is \geq Day 149.

Data from all assessments (scheduled and unscheduled), including multiple assessments, will be included in listings.

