19. CCI

20. Not collected for patients who prematurely discontinue from the double-masked Treatment Period.
21. For those patients who have consented, photographs of the patient's eyes will be taken prior to the first infusion and at Week 24 (all patients) and Week 48 (non-responders who elect to receive open-label TEPEZZA).
22. For non-responders who choose to receive open-label treatment, TEPEZZA infusion will be performed at Week 24 (first of 8 infusions). All Week 24 assessments except AE and concomitant medication monitoring, post-infusion PK sample collection and 24-hour post-dose phone/email contact must be completed prior to TEPEZZA infusion.
23. Phone (or email) contact by research staff focusing on safety and tolerability aspects will be made the day after infusion for the first and second infusions during the double-masked Treatment Period and during the open-label Treatment Period, and thereafter as deemed appropriate. In addition, patients who experience an infusion-associated event after any subsequent infusion will also be contacted by phone (or email) by research staff the day after the infusion, and thereafter as deemed appropriate.

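### The Week 24 analysis window closes at Day 179 only for patients who enter open label, so a late but valid pre-dose reading drops out of their primary analysis

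*SAP*

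**What the plan says.** **Windows.** SAP Section 5.4.3 maps every reading after the first dose to an analysis visit by study day, so that "every observation (unscheduled visits included) collected can be allocated to the scheduled analysis visit". Table 1 gives Week 24 a target of Day 169 and a range of Day 149 to 179, and gives Week 27 Day 180 to 200. The footnote to the Week 24 row reads "For patients who did not enter the open-label treatment period, Week 24 analysis visit window is" Day 149 or later.

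**Choice within a window.** If several readings fall in one window, "the closest non-missing valid assessment to the scheduled day will be used in the analysis". For ties, "If 2 non-missing assessment actual dates are equidistant from the target day, the later visit will be used in the analysis".

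**Who enters open label.** SAP Section 3.1: "Proptosis non-responders who have completed the double-masked treatment period may choose to receive 8 infusions of TEPEZZA". Entry is optional.

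**Timing.** The Week 24 visit is allowed plus or minus "7 days for Week 24 of double-masked treatment period" (SAP Figure 1, note 2). For entrants, "TEPEZZA infusion will be performed at Week 24 (first of 8 infusions"), and the Week 24 assessments, apart from a few listed safety and PK items, "must be completed prior to TEPEZZA infusion" (SAP Section 15.1, footnote 22).

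**Analyses.** The primary model (SAP Section 9.2.1) uses Weeks 3, 6, 12, 18 and 24 only. The main responder analysis counts a missing Week 24 as non-response and is then repeated on observed results (Section 9.3.1.1). Section 4.2 restricts primary efficacy data to the period from Screening to the Week 24 visit, and Section 9 restricts it to double-masked data.

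**The concern.** Two patients have the same late Week 24 visit, say on Day 181. One does not enter open label, and the reading is used as Week 24. The other is a non-responder who enters. That reading was also taken before the first open-label infusion, so it is double-masked data, but Table 1 calls it Week 27 and the primary model has no Week 24 value for the patient. The footnote is keyed to open-label entry, and entry is open only to non-responders. The values at risk of removal are therefore all from patients with less than 2 mm improvement in the study eye or deterioration in the fellow eye. Missingness that depends on the Week 24 outcome is not what a mixed model with ignorable missing data assumes. It also sits badly with a treatment-policy estimand based on observed data (Section 9.1).

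There is a smaller gap in the other direction. Day 179 is a calendar limit and is not tied to dosing. For an entrant dosed on time, the Week 24 window stays open after the first open-label infusion.

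**Working it through.** **1. Planning figures (SAP Section 5.1).** 38 and 19 patients, difference 2.0 mm, SD 2.5 mm, two-sided 0.05.
- SE = 2.5 × √(1/38 + 1/19) = 0.70 mm.
- Power by the normal approximation is 81.3% (79.9% by noncentral t). The stated 81% is reproduced and is not in dispute.

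**2. Where Day 179 comes from.** The midpoint of targets 169 and 190 is (169 + 190)/2 = 179.5. Most neighbouring limits are built the same way, so Day 179 carries no information about dosing.

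**3. When a reading is lost.** The permitted visit range is 169 ± 7, or Day 162 to 176. Loss needs Day 180 or later: 11 days past target and 4 days outside the permitted range.

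**4. Effect on the primary estimate (assumed inputs).** Week 24 mean changes −2.5 and −0.5 mm, SD 2.5, adjacent-visit correlation 0.75, and late visits in 5 to 30% of patients. Week 24 was removed for every late non-responder, with regression on earlier visits standing in for the mixed model (400,000 simulated patients per arm).
- Shift in the treatment difference: 0.002 to 0.015 mm. A rerun gave values within this range. Both arm means move in the same direction, so most of the shift cancels.
- Worst case against the SE: 0.015/0.70 ≈ 2%.

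**5. Effect on responder rates.** In the main analysis there is none: a lost value from a non-responder is still scored as non-response. In the repeat on observed results, with true rate r, late fraction p and every non-responder entering, the observed rate is r / [r + (1 − p)(1 − r)]. With p = 0.20:
- TEPEZZA: 0.580/(0.580 + 0.8 × 0.420) = 0.580/0.916 = 63.32%, up from 58.0%.
- Placebo: 0.274/(0.274 + 0.8 × 0.726) = 0.274/0.8548 = 32.05%, up from 27.4%.
- Difference: 30.6 points before, 63.32 − 32.05 = 31.3 points after.

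Over p = 0.05 to 0.30 each arm rises by about 1 to 8 points. The rates ignore the fellow-eye condition.

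**6. Post-dose readings.** Take a pre-dose Week 24 reading and first open-label infusion on Day d (162 to 176), and one unscheduled post-dose reading on Day u (d + 1 to 179).
- Eligible day pairs: 17 + 16 + … + 3 = 150.
- Pairs in which the post-dose reading is selected (nearer Day 169, or tied and later): 14 + 12 + 10 + 8 + 6 + 4 + 2 = 56, all with d from 162 to 168. A pre-dose reading on Day 162 loses to any later one on Day 163 to 176.
- This counts possibilities and is not a probability. An on-time Week 27 visit never qualifies: the earliest, counted from a Day 162 visit, is 162 + 21 − 3 = Day 180.
- Closing the window at the first open-label infusion reduces both counts to 0.

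**7. Knock-on in open label.** Suppose a placebo patient is first dosed open-label on Day 181 and visits stay three weeks apart. The Day 181 reading is both TEPEZZA Baseline (Section 5.4.2) and Week 27, giving a change of zero. The actual three-week reading (Day 202) falls in the Week 30 window (Day 201 to 232). There it beats the actual six-week reading (Day 223), being 9 rather than 12 days from Day 211.

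**The case against.** The strongest reply is that this is immaterial and partly covered elsewhere. Most of it stands. Loss requires a visit deviation of at least 4 days, and the documents give no late-visit rate, so 30% is a stress test. The responder figures assume that every non-responder enters, although entry is optional. An affected patient still contributes earlier visits to the primary model.

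A reader might infer that the window is defined by response and that the primary result is therefore materially biased. The documents do not support that. The trigger is entry, non-responders who decline keep their late values, and the calculated shift is negligible.

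A reader might also infer that active drug contaminates the placebo Week 24 values. That is remote. It needs an unscheduled proptosis measurement after dosing, a Week 24 visit before Day 169, and a program that does not apply the limits in Sections 4.2 and 9.

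Two things remain. Sections 4.2 and 9 state a scope, but no window rule carries it out, whereas Section 10.1 does state the first open-label dose as a boundary for adverse events. And neither section restores a late pre-dose reading that Table 1 has labelled Week 27.

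**Conclusion.** The point holds as a minor defect in the window rules. Table 1 treats identical late, pre-dose Week 24 readings differently according to open-label entry, and those removed can only be from non-responders. The expected shift in the primary treatment difference is about 0.002 to 0.015 mm, against a planned 2.0 mm and a standard error of 0.70 mm. This rests on assumed means, correlation and late-visit rates of 5 to 30%. The main responder test does not move. The repeat on observed results overstates both arms' rates and leaves the difference almost unchanged. Selection of a post-dose reading as Week 24 is possible under the window rules but would be rare. Neither problem threatens the trial's conclusion. The case for correcting them is that valid double-masked data should not depend on a calendar cut, and that an outcome-linked window is awkward to defend after unmasking.

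**What to change.** In SAP Table 1, replace the Day 179 limit for open-label entrants: Week 24 is taken from readings on Day 149 up to, and before, the first open-label infusion, with readings after that infusion excluded. Keep the open-ended window for non-entrants.

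Count the Week 27 and later windows from the date of the first open-label infusion, so that late entrants' visits are not moved into the wrong window. The existing TEPEZZA Study Day (Section 5.4.1) will not serve for everyone, because for patients randomized to TEPEZZA it starts at their first double-masked dose.

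The cost is a footnote, a date condition in the program using a date already recorded, and re-anchored open-label windows, which feed descriptive summaries only. Sample size, power and trial conduct do not change. The change should be made before the double-masked database is unmasked.
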